2.4 Follow-up evaluation of target and non-target lesions

To assess tumor response, the sum of diameters for all target lesions will be calculated (at baseline and throughout the study). At each assessment response is evaluated first separately for the target ([Table 2-1](#)) and non-target lesions ([Table 2-2](#)) identified at baseline. These evaluations are then used to calculate the overall lesion response considering both the target and non-target lesions together ([Table 2-3](#)) as well as the presence or absence of new lesions.

2.4.1 Follow-up and recording of lesions

At each visit and for each lesion the actual date of the scan or procedure which was used for the evaluation of each specific lesion should be recorded. This applies to target and non-target lesions as well as new lesions that are detected. At the assessment visit all of the separate lesion evaluation data are examined by the investigator in order to derive the overall visit response. Therefore all such data applicable to a particular visit should be associated with the same assessment number.

2.4.1.1 Non-nodal lesions

Following treatment, lesions may have longest diameter measurements smaller than the image reconstruction interval. Lesions smaller than twice the reconstruction interval are subject to substantial “partial volume” effects (i.e., size may be underestimated because of the distance of the cut from the longest diameter; such lesions may appear to have responded or progressed on subsequent examinations, when, in fact, they remain the same size).

If the lesion has completely disappeared, the lesion size should be reported as 0 mm.

Measurements of non-nodal target lesions that become 5 mm or less in longest diameter are likely to be non-reproducible. Therefore, it is recommended to report a default value of 5 mm, instead of the actual measurement. This default value is derived from the 5 mm CT slice thickness (but should not be changed with varying CT slice thickness). Actual measurement should be given for all lesions larger than 5 mm in longest diameter irrespective of slice thickness/reconstruction interval.

[figure not shown]
In other cases where the lesion cannot be reliably measured for reasons other than its size (e.g., borders of the lesion are confounded by neighboring anatomical structures), no measurement should be entered and the lesion cannot be evaluated.

2.4.1.2 Nodal lesions

A nodal lesion less than 10 mm in size by short axis is considered normal. Lymph nodes are not expected to disappear completely, so a “non-zero size” will always persist.

Measurements of nodal target lesions that become 5 mm or less in short axis are likely to be non-reproducible. Therefore, it is recommended to report a default value of 5 mm, instead of the actual measurement. This default value is derived from the 5 mm CT slice thickness (but should not be changed with varying CT slice thickness). Actual measurement should be given for all lesions larger than 5 mm in short axis irrespective of slice thickness/reconstruction interval.

However, once a target nodal lesion shrinks to less than 10 mm in its short axis, it will be considered normal for response purpose determination. The lymph node measurements will continue to be recorded to allow the values to be included in the sum of diameters for target lesions, which may be required subsequently for response determination.

2.4.2 Determination of target lesion response

Table 2-1 Response criteria for target lesions

Response Criteria	Evaluation of target lesions
Complete Response (CR):	Disappearance of all non-nodal target lesions. In addition, any pathological lymph nodes assigned as target lesions must have a reduction in short axis to < 10 mm ¹
Partial Response (PR):	At least a 30% decrease in the sum of diameter of all target lesions, taking as reference the baseline sum of diameters.
Progressive Disease (PD):	At least a 20% increase in the sum of diameter of all measured target lesions, taking as reference the smallest sum of diameter of all target lesions recorded at or after baseline. In addition to the relative increase of 20%, the sum must also demonstrate an absolute increase of at least 5 mm ² .
Stable Disease (SD):	Neither sufficient shrinkage to qualify for PR or CR nor an increase in lesions which would qualify for PD.
Unknown (UNK)	Progression has not been documented and one or more target lesions have not been assessed or have been assessed using a different method than baseline. ³

1. SOD for CR may not be zero when nodal lesions are part of target lesions

[figure not shown]
2. Following an initial CR, a PD cannot be assigned if all non-nodal target lesions are still not present and all nodal lesions are <10 mm in size. In this case, the target lesion response is CR

3. Methodology change See [Section 2.2](#).

Notes on target lesion response

[figure not shown]
Reappearance of lesions: If the lesion appears at the same anatomical location where a target lesion had previously disappeared, it is advised that the time point of lesion disappearance (i.e., the “0 mm” recording) be re-evaluated to make sure that the lesion was not actually present and/or not visualized for technical reasons in this previous assessment. If it is not possible to change the 0 value, then the investigator/radiologist has to decide between the following three possibilities:

- The lesion is a new lesion, in which case the overall tumor assessment will be considered as progressive disease
- The lesion is clearly a reappearance of a previously disappeared lesion, in which case the size of the lesion has to be entered in the CRF and the tumor assessment will remain based on the sum of tumor measurements as presented in [Table 2-1](#) above (i.e., a PD will be determined if there is at least 20% increase in the sum of diameters of **all** measured target lesions, taking as reference the smallest sum of diameters of all target lesions recorded at or after baseline with at least 5 mm increase in the absolute sum of the diameters). Proper documentation should be available to support this decision. This applies to patients who have not achieved target response of CR. For patients who have achieved CR, please refer to last bullet in this section.
- For those patients who have only one target lesion at baseline, the reappearance of the target lesion which disappeared previously, even if still small, is considered a PD.
- Missing measurements: In cases where measurements are missing for one or more target lesions it is sometimes still possible to assign PD based on the measurements of the remaining lesions. For example, if the sum of diameters for 5 target lesions at baseline is 100 mm at baseline and the sum of diameters for 3 of those lesions at a post-baseline visit is 140 mm (with data for 2 other lesions missing) then a PD should be assigned. However,

in other cases where a PD cannot definitely be attributed, the target lesion response would be UNK.

- Nodal lesion decrease to normal size: When nodal disease is included in the sum of target lesions and the nodes decrease to “normal” size they should still have a measurement recorded on scans. This measurement should be reported even when the nodes are normal in order not to overstate progression should it be based on increase in the size of nodes.
- Lesions split: In some circumstances, disease that is measurable as a target lesion at baseline and appears to be one mass can split to become two or more smaller sub-lesions. When this occurs, the diameters (long axis - non-nodal lesion, short axis - nodal lesions) of the two split lesions should be added together and the sum recorded in the diameter field on the case report form under the original lesion number. This value will be included in the sum of diameters when deriving target lesion response. The individual split lesions will not be considered as new lesions, and will not automatically trigger a PD designation.
- Lesions coalesced: Conversely, it is also possible that two or more lesions which were distinctly separate at baseline become confluent at subsequent visits. When this occurs a plane between the original lesions may be maintained that would aid in obtaining diameter measurements of each individual lesion. If the lesions have truly coalesced such that they are no longer separable, the maximal diameters (long axis - non-nodal lesion, short axis - nodal lesions) of the “merged lesion” should be used when calculating the sum of diameters for target lesions. On the case report form, the diameter of the “merged lesion” should be recorded for the size of one of the original lesions while a size of “0”mm should be entered for the remaining lesion numbers which have coalesced.
- The **measurements for nodal lesions**, even if less than 10 mm in size, will contribute to the calculation of target lesion response in the usual way with slight modifications.
- Since lesions less than 10 mm are considered normal, a CR for target lesion response should be assigned when all nodal target lesions shrink to less than 10 mm and all non-nodal target lesions have disappeared.
- Once a CR target lesion response has been assigned a CR will continue to be appropriate (in the absence of missing data) until progression of target lesions.
- Following a CR, a PD can subsequently only be assigned for target lesion response if either a non-nodal target lesion “reappears” or if any single nodal lesion is at least 10 mm and there is at least 20% increase in sum of the diameters of all nodal target lesions relative to nadir with at least 5 mm increase in the absolute sum of the diameters.

2.4.3 Determination of non-target lesion response

Table 2-2 Response criteria for non-target lesions

Response Criteria	Evaluation of non-target lesions
Complete Response (CR):	Disappearance of all non-target lesions. In addition, all lymph nodes assigned a non-target lesions must be non-pathological in size (< 10 mm short axis)
Progressive Disease (PD):	Unequivocal progression of existing non-target lesions. ¹
Non-CR/Non-PD:	Neither CR nor PD
Unknown (UNK)	Progression has not been documented and one or more non-target lesions have not been assessed or have been assessed using a different method than baseline.

¹ Although a clear progression of non-target lesions only is exceptional, in such circumstances, the opinion of the treating physician does prevail and the progression status should be confirmed later on by the review panel (or study chair).

[figure not shown]
Notes on non-target lesion response

- The response for non-target lesions is **CR** only if all non-target non-nodal lesions which were evaluated at baseline are now all absent and with all non-target nodal lesions returned to normal size (i.e. < 10 mm). If any of the non-target lesions are still present, or there are any abnormal nodal lesions (i.e. ≥ 10 mm) the response can only be ‘**Non-CR/Non-PD**’ unless any of the lesions was not assessed (in which case response is **UNK**) or there is unequivocal progression of the non-target lesions (in which case response is **PD**).
- Unequivocal progression: To achieve “unequivocal progression” on the basis of non-target disease there must be an overall level of substantial worsening in non-target disease such that, even in presence of CR, PR or SD in target disease, the overall tumor burden has increased sufficiently to merit discontinuation of therapy. A modest “increase” in the size of one or more non-target lesions is usually not sufficient to qualify for unequivocal progression status. The designation of overall progression solely on the basis of change in non-target disease in the face of CR, PR or SD of target disease is therefore expected to be rare. In order for a PD to be assigned on the basis of non-target lesions, the increase in the extent of the disease must be substantial even in cases where there is no measurable disease at baseline. If there is unequivocal progression of non-target lesion(s), then at least one of the non-target lesions must be assigned a status of “Worsened”. Where possible, similar rules to those described in [Section 2.4.2](#) for assigning PD following a CR for the non-target lesion response in the presence of non-target lesions nodal lesions should be applied.

2.4.4 New lesions

The appearance of a new lesion is always associated with Progressive Disease (PD) and has to be recorded as a new lesion in the New Lesion CRF page.

- If a new lesion is **equivocal**, for example because of its small size, continued therapy and follow-up evaluation will clarify if it represents truly new disease. If repeat scans confirm there is definitely a new lesion, then progression should be declared using the date of the first observation of the lesion

- If new disease is observed in a region which was **not scanned at baseline** or where the particular baseline scan is not available for some reason, then this should be considered as a PD. The one exception to this is when there are no baseline scans at all available for a patient in which case the response should be UNK, as for any of this patient's assessment (see [Section 2.5](#)).
- A **lymph node is considered as a “new lesion”** and, therefore, indicative of progressive disease if the short axis increases in size to ≥ 10 mm for the first time in the study plus 5 mm absolute increase.
FDG-PET: can complement CT scans in assessing progression (particularly possible for ‘new’ disease). See [Section 2.2](#).

2.5 Evaluation of overall lesion response

The evaluation of overall lesion response at each assessment is a composite of the target lesion response, non-target lesion response and presence of new lesions as shown below in [Table 2-3](#).

Table 2-3 Overall lesion response at each assessment

Target lesions	Non-target lesions	New Lesions	Overall lesion response
CR	CR	No	CR ¹
CR	Non-CR/Non-PD ³	No	PR
CR, PR, SD	UNK	No	UNK
PR	Non-PD and not UNK	No	PR ¹
SD	Non-PD and not UNK	No	SD ^{1, 2}
UNK	Non-PD or UNK	No	UNK ¹
PD	Any	Yes or No	PD
Any	PD	Yes or No	PD
Any	Any	Yes	PD

1. This overall lesion response also applies when there are no non-target lesions identified at baseline.

2. Once confirmed PR was achieved, all these assessments are considered PR.

3. As defined in [Section 2.4](#).

[figure not shown]
If there are no baseline scans available at all, then the overall lesion response at each assessment should be considered Unknown (UNK).

If the evaluation of any of the target or non-target lesions identified at baseline could not be made during follow-up, the overall status must be ‘unknown’ unless progression was seen.

In some circumstances it may be difficult to distinguish residual disease from normal tissue. When the evaluation of complete response depends on this determination, it is recommended that the residual lesion be investigated (fine needle aspirate/biopsy) to confirm the CR.

3 Efficacy definitions

The following definitions primarily relate to patients who have measurable disease at baseline. [Section 3.2.8](#) outlines the special considerations that need to be given to patients with no measurable disease at baseline in order to apply the same concepts.

3.1 Best overall response

The best overall response is the best response recorded from the start of the treatment until disease progression/recurrence (taking as reference for PD the smallest measurements recorded since the treatment started). In general, the patient's best response assignment will depend on the achievement of both measurement and confirmation criteria.

The best overall response will usually be determined from response assessments undertaken while on treatment. However, if any assessments occur after treatment withdrawal the protocol should specifically describe if these will be included in the determination of best overall response and/or whether these additional assessments will be required for sensitivity or supportive analyses. As a default, any assessments taken more than 30 days after the last dose of study treatment will not be included in the best overall response derivation. If any alternative cancer therapy is taken while on study any subsequent assessments would ordinarily be excluded from the best overall response determination. If response assessments taken after withdrawal from study treatment and/or alternative therapy are to be included in the main endpoint determination, then this should be described and justified in the protocol.

Where a study requires confirmation of response (PR or CR), changes in tumor measurements must be confirmed by repeat assessments that should be performed not less than 4 weeks after the criteria for response are first met.

[figure not shown]
Longer intervals may also be appropriate. However, this must be clearly stated in the protocol. The main goal of confirmation of objective response is to avoid overestimating the response rate observed. In cases where confirmation of response is not feasible, it should be made clear when reporting the outcome of such studies that the responses are not confirmed.

- For non-randomized trials where response is the primary endpoint, confirmation is needed.
- For trials intended to support accelerated approval, confirmation is needed
- For all other trials, confirmation of response may be considered optional.

The best overall response for each patient is determined from the sequence of overall (lesion) responses according to the following rules:

- CR = at least two determinations of CR at least 4 weeks apart before progression where confirmation required or one determination of CR prior to progression where confirmation not required
- PR = at least two determinations of PR or better at least 4 weeks apart before progression (and not qualifying for a CR) where confirmation required or one determination of PR prior to progression where confirmation not required
- SD = at least one SD assessment (or better) > 6 weeks after randomization/start of treatment (and not qualifying for CR or PR).
- PD = progression \leq 12 weeks after randomization/ start of treatment (and not qualifying for CR, PR or SD).
- UNK = all other cases (i.e. not qualifying for confirmed CR or PR and without SD after more than 6 weeks or early progression within the first 12 weeks)

Overall lesion responses of CR must stay the same until progression sets in, with the exception of a UNK status. A patient who had a CR cannot subsequently have a lower status

other than a PD, e.g. PR or SD, as this would imply a progression based on one or more lesions reappearing, in which case the status would become a PD.

Once an overall lesion response of PR is observed (which may have to be a confirmed PR depending on the study) this assignment must stay the same or improve over time until progression sets in, with the exception of an UNK status. However, in studies where confirmation of response is required, if a patient has a single PR ($\geq 30\%$ reduction of tumor burden compared to baseline) at one assessment, followed by a $< 30\%$ reduction from baseline at the next assessment (but not $\geq 20\%$ increase from previous smallest sum), the objective status at that assessment should be SD. Once a confirmed PR was seen, the overall lesion response should be considered PR (or UNK) until progression is documented or the lesions totally disappear in which case a CR assignment is applicable. In studies where confirmation of response is not required after a single PR the overall lesion response should still be considered PR (or UNK) until progression is documented or the lesion totally disappears in which case a CR assignment is applicable.

Example: In a case where confirmation of response is required the sum of lesion diameters is 200 mm at baseline and then 140 mm - 150 mm - 140 mm - 160 mm - 160 mm at the subsequent visits. Assuming that non-target lesions did not progress, the overall lesion response would be PR - SD - PR - PR - PR. The second assessment with 140 mm confirms the PR for this patient. All subsequent assessments are considered PR even if tumor measurements decrease only by 20% compared to baseline (200 mm to 160 mm) at the following assessments.

If the patient progressed but continues study treatment, further assessments are not considered for the determination of best overall response.

Note: these cases may be described as a separate finding in the CSR but not included in the overall response or disease control rates.

The best overall response for a patient is always calculated, based on the sequence of overall lesion responses. However, the overall lesion response at a given assessment may be provided from different sources:

- Investigator overall lesion response
- Central Blinded Review overall lesion response
- Novartis calculated overall lesion response (based on measurements from either Investigator or Central Review)

The primary analysis of the best overall response will be based on the sequence of investigator/central blinded review/calculated (investigator)/calculated (central) overall lesion responses.

Based on the patients' best overall response during the study, the following rates are then calculated:

Overall response rate (ORR) is the proportion of patients with a best overall response of CR or PR. This is also referred to as 'Objective response rate' in some protocols or publications.

Disease control rate (DCR) is the proportion of patients with a best overall response of CR or PR or SD.

Another approach is to summarize the progression rate at a certain time point after baseline. In this case, the following definition is used:

Early progression rate (EPR) is the proportion of patients with progressive disease within 8 weeks of the start of treatment.

The protocol should define populations for which these will be calculated. The timepoint for EPR is study specific. EPR is used for the multinomial designs of [Dent and Zee \(2001\)](#) and counts all patients who at the specified assessment (in this example the assessment would be at 8 weeks \pm window) do not have an overall lesion response of SD, PR or CR. Patients with an unknown (UNK) assessment at that time point and no PD before, will not be counted as early progressors in the analysis but may be included in the denominator of the EPR rate, depending on the analysis population used. Similarly when examining overall response and disease control, patients with a best overall response assessment of unknown (UNK) will not be regarded as “responders” but may be included in the denominator for ORR and DCR calculation depending on the analysis population (e.g. populations based on an ITT approach).

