4.1 Description of study design

This is a phase 1, multi-center, open-label study, with a dose escalation part followed by an expansion part. Eligible patients aged 12 months to 21 years old whose tumor has progressed following standard therapy, or for which no standard, effective therapy exists will be enrolled in the study. LEE011 will be administered orally, once daily for 21 days followed by a 1 week break (28-day cycle) at the starting dose of 280 mg/m²/d.. For the purpose of scheduling assessments and establishing the MTD/RDE, a cycle is defined as 28 days in length.

During the dose escalation part, 3-6 newly enrolled patients in successive cohorts will receive increasing doses of LEE011 with the dosing schedule specified above. A BLRM using the EWOC principle will be used to guide dose escalation. During the course of dose escalation, additional patients may be enrolled to previously tested lower dose levels that have been assessed as safe and well-tolerated if there is no slot available in the current cohort under testing. It is expected that approximately 10 patients may be enrolled and treated within this context. In all, it is anticipated that approximately 28 patients will be treated during the escalation part.

Once the MTD/RDE has been determined, the expansion part will begin to better characterize the safety, tolerability and PK profile of LEE011, as well as assess preliminary antitumor activity of LEE011. During the expansion part of the study LEE011 will be dosed at the MTD, or at a lower RDE, if the available data suggest that the MTD is not appropriate for multiple cycles of therapy. This part will include 2 arms, one restricted to neuroblastoma patients and the second to MRT patients with either CNS or extra-CNS primary. A minimum of 8 patients each will be required for CNS and extra-CNS primary MRT. Enrollment will proceed in parallel. Patients enrolled during the expansion part of the study are required to have measurable disease. Approximately 18 patients will be treated in each arm, for a total of approximately 36 patients in the expansion part.

[figure not shown]

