Subsequent tumor evaluations will be performed on Day 22 (± 7 days) of cycles 2, 4 and 6. After cycle 6 tumor evaluations will be performed on Day 22 (± 7 days) of every 4th cycle (e.g., C10, C14, C18), or sooner if there is clinical evidence of disease progression. Tumor evaluations will also be performed at EOT. If the last prior tumor evaluation was within 28 days of EOT or objective evidence of progressive disease has already been documented, then tumor evaluations do not need to be repeated at EOT.

Tumor evaluations after the screening assessment will include evaluation of all sites of disease identified at baseline, using the same technique that was used at screening. If there was no evidence of disease in a body region at screening, that region does not need to be imaged at subsequent assessments, unless there is clinical concern for a new lesion in that body region. Bone marrow aspirate and/or biopsies and MIBG scans are not required after baseline if they were negative at screening.

The CSF test is required for primary CNS tumors (including MRT) patients at screening and is performed per institutional standards. If sampling is not feasible, patients may still enroll in study after discussion with Novartis and the investigator. Information will be collected if performed. CSF will be performed at Screening and if positive at screening, subsequent measurements are performed only for confirmation of CR as needed on Day 22 (± 7 days) of cycles 2, 4 and 6. After cycle 6 tumor evaluations, CSF test will be performed as needed on Day 22 (± 7 days) of every 4th cycle (e.g., C10, C14, C18), or sooner if there is clinical evidence of disease progression. Only 2 negative sequential CSF cytology are required for establishing CR.

All radiological assessments obtained for all patients enrolled during the study will be centrally collected and subjected to quality checks by an imaging CRO selected by Novartis. The site manual provided by the designated imaging CRO will provide further details regarding image collection.

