10.6.1.3.2 Basic tables, figures and listings

Relationship between MYCN (neuroblastoma), [REDACTED] (MRT), other genetic alterations and anti-tumor activity at the MTD/RDE will be presented using two way tables of best overall response. Moreover, the panel of assessed genes known to be genetically altered at a frequency of at least 5% in our study population will also be listed.

Pharmacodynamic assessments of LEE011 will be evaluated by pre and post treatment bone marrow aspirate/biopsy samples analyzed for [REDACTED] and [REDACTED]. Absolute and/or relative (%) changes from baseline will be listed by subject and summarized using descriptive statistics by treatment and by visit for each biomarker. Longitudinal plots showing patient level and mean changes may also be generated.

[REDACTED] collected from archival tumor samples will be listed.

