3.2.9 Sensitivity analyses

This section outlines the possible event and censoring dates for progression, as well as addresses the issues of missing tumor assessments during the study. For instance, if one or more assessment visits are missed prior to the progression event, to what date should the progression event be assigned? And should progression event be ignored if it occurred after a long period of a patient being lost to follow-up? It is important that the protocol and RAP specify the primary analysis in detail with respect to the definition of event and censoring dates and also include a description of one or more sensitivity analyses to be performed.

Based on definitions outlined in [Section 3.2.7](#), and using the draft FDA guideline on endpoints (Clinical Trial Endpoints for the Approval of Cancer Drugs and Biologics, April 2005) as a reference, the following analyses can be considered:

[REDACTED]

Table 3-2 Options for event dates used in PFS, TTP, duration of response

Situation		Options for end-date (progression or censoring) ¹ (1) = default unless specified differently in the protocol or RAP	Outcome
A	No baseline assessment	(1) Date of randomization/start of treatment ³	Censored
B	Progression at or before next scheduled assessment	(1) Date of progression (2) Date of next scheduled assessment ²	Progressed Progressed
C1	Progression or death after exactly one missing assessment	(1) Date of progression (or death) (2) Date of next scheduled assessment ²	Progressed Progressed
C2	Progression or death after two or more missing assessments	(1) Date of last adequate assessment ² (2) Date of next scheduled assessment ² (3) Date of progression (or death)	Censored Progressed Progressed
D	No progression	(1) Date of last adequate assessment	Censored
E	Treatment discontinuation due to 'Disease progression' without documented progression, i.e. clinical progression based on investigator claim	(1) N/A (2) Date of discontinuation (visit date at which clinical progression was determined)	Ignored Progressed
F	New anticancer therapy given	(1) Date of last adequate assessment (2) Date of secondary anti-cancer therapy (3) Date of secondary anti-cancer therapy (4) N/A	Censored Censored Event Ignored
G	Deaths due to reason other than deterioration of 'Study indication'	(1) Date of last adequate assessment	Censored (only TTP and duration of response)

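### Best overall response can be PD only up to week 12, but the second scheduled scan is at week 15, so progression first documented there after an unusable first scan is labelled UNK

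*Protocol*

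**What the plan says.** Appendix 1, section 3.1, derives best overall response from the sequence of visit responses.

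- PD requires progression no later than "12 weeks after randomization/ start of treatment (and not qualifying for CR, PR or SD".
- SD requires at least one SD or better more than 6 weeks after the start.
- UNK takes every remaining case, described as "not qualifying for confirmed CR or PR and without SD after more than 6 weeks or early progression within the first 12 weeks".

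On timing, protocol section 4.1 states that "a cycle is defined as 28 days in length", and section 7.2.1 states: "Subsequent tumor evaluations will be performed on Day 22 (± 7 days) of cycles 2, 4 and 6". After cycle 6 the scans come every fourth cycle, "or sooner if there is clinical evidence of disease progression". Section 7.2.1 also requires a tumor evaluation at EOT, unless one was done within the preceding 28 days or progression is already documented.

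For TTP, Table 3-2 in Appendix 1 (section 3.2.9) covers the situation "Progression or death after exactly one missing assessment" (C1). Its default option counts the patient as progressed on the actual date.

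Best overall response feeds ORR (section 10.5.4). It also feeds the biomarker displays of section 10.6.1.3.2, which "will be presented using two way tables of best overall response" at the MTD/RDE.

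Appendix 1, sections 4.1 and 4.5.5, expects study-specific choices to be made in the protocol or RAP and the standard programs to be adapted. Neither the protocol body nor the SAP adapts the 12-week limit.

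**The concern.** A 12-week limit on PD works when the second scan falls inside it. Here it does not: the limit lies between the first and second scheduled scans. For a patient on the planned schedule, only the first scan can yield a best overall response of PD. If that scan is missed or unusable, progression seen clearly at the next one has no category except UNK.

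An unusable visit needs no unusual event. Under Appendix 1, section 2.5, one lesion that cannot be evaluated makes the visit unknown unless progression was seen. Under section 2.2, a change of contrast use or technique does so by default.

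What is at stake is how documented progression is described. In a summary of best overall response, or a cross-tabulation of response by genetic alteration, a tumor known to have progressed on treatment would look like missing data. In small groups one such patient is visible.

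**Working it through.** The plan gives no week numbers for its scans, so there is no stated figure to reproduce.

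**Inputs.** Cycle length 28 days (section 4.1). Scans on Day 22 ± 7 days of cycles 2 and 4 (section 7.2.1). PD limit 12 weeks and SD minimum of more than 6 weeks (Appendix 1, section 3.1). Programming rule: end date minus start date plus 1 (Appendix 1, section 4.5.1).

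**Step 1: scan days.** Study day = (cycle − 1) × 28 + 22. Elapsed weeks = (day − 1)/7.

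| Scan | Study day | Window | Elapsed weeks (window) | Weeks with the +1 rule (window) |
|---|---|---|---|---|
| C2D22 | 28 + 22 = 50 | 43-57 | 7.0 (6.0-8.0) | 7.1 (6.1-8.1) |
| C4D22 | 84 + 22 = 106 | 99-113 | 15.0 (14.0-16.0) | 15.1 (14.1-16.1) |

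**Step 2: the limit.** 12 × 7 = 84 days. No scheduled scan lies between day 57 and day 99. The earliest in-window second scan is at 14.0 weeks, two weeks past the limit.

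**Step 3: the section 3.1 rules applied to response sequences** (12-week limit, same result under both day counts).

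| Sequence | Best overall response |
|---|---|
| UNK at day 50, PD at day 99, 106 or 113 | UNK in each case |
| First scan missed, PD at day 106 | UNK |
| PD at day 50 | PD |
| SD at day 50, PD at day 106 | SD |
| UNK at day 50, PD on an unscheduled scan at day 80 | PD |

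**Step 4: effect on the endpoints.**

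- ORR: PD and UNK are both non-responses, so the rate is unchanged with the default FAS denominator (section 10.1.1). Appendix 1, section 3.1, leaves inclusion of UNK in the denominator to the analysis population. If one UNK patient were dropped from an illustrative arm of 18 with one responder, ORR would move from 1/18 = 5.6% (exact 95% CI 0.1-27.3%) to 1/17 = 5.9% (0.1-28.7%).
- TTP: an event on the date of progression, under the Table 3-2 default.
- DOR: defined for responders only, so not involved.

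**Step 5: the limit that would cover the second scan.** Day 113 is 112/7 = 16.0 elapsed weeks, or 113/7 = 16.14 weeks with the +1 rule. A 16-week limit covers days 99 and 106 under both counts, but day 113 only on elapsed time. A 17-week limit (119 days) covers all three under both.

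**The case against.** The strongest defense is that UNK is an honest label. With no usable scan until week 15, nobody knows whether the tumor was stable after week 6, which would have made the patient SD. TTP and best overall response ask different questions, so an event in one and unknown in the other need not conflict. This stands in part: the choice is a convention, and a reader who infers a contradiction between endpoints goes too far. But the defense does not explain a limit that excludes the second scheduled scan. The first two evaluations are the natural span for early progression on this schedule.

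Some cases are rescued. An EOT or earlier unscheduled scan showing PD by week 12 gives PD. Appendix 1 lets clinicians re-evaluate UNK visits (section 4.4), allows a justified definitive assessment despite a method change (section 2.2), and allows PD from the remaining lesions (section 2.4.2). So a reader should not infer that the result is beyond all discretion. None of these routes helps once the first scan is missing or remains UNK and nothing else is imaged by week 12.

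A reader might also infer that dose delays could push even the first scan past week 12 (50 + 35 = day 85). The documents do not support that. Sections 4.1 and 7.1.2 fix the cycle at 28 days for scheduling, and no passage says that scans move with interrupted dosing.

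Finally, the primary CSR RAP Module 3, to which the SAP defers, may already set another limit. It is not available here.

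**Conclusion.** The point holds as a minor mismatch between a generic rule and this trial's scan schedule. It applies only when three conditions are met: the first scan is missing or remains UNK, no other scan shows PD by week 12, and PD is documented at the second scheduled scan. For such a patient the written rule gives UNK anywhere in the scan window and under either day count. It affects the PD/UNK split in best overall response and the exploratory two-way biomarker tables. It does not affect ORR on the FAS, TTP or DOR.

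A reader might infer a number from the 36 planned expansion patients. Assuming that 5-15% of first scans are unusable and 50-100% of those patients progress by C4, the result is 36 × 0.05 × 0.5 = 0.9 to 36 × 0.15 × 1.0 = 5.4 patients. That range should not be relied on. Both rates are assumptions, and the SAP (sections 2.5.4 and 4) says that enrollment was halted and analyses cover dose escalation only. The final CSR plans no secondary efficacy analysis (section 2.7) and no biomarker analysis (section 2.12), so the point bears on outputs governed by the primary CSR RAP. The supportable statement is that few patients are likely to be affected and that the number cannot be fixed from these documents.

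**What to change.** In section 10.5.4 or the RAP, adapt the limit to this schedule. Define PD as documented progression at or before the second scheduled tumor evaluation including its window (C4D22 + 7 days, day 113), in a patient not qualifying for CR, PR or SD. A 17-week limit does this under either day count. Change the UNK definition to match. State the day count as well, because an SD scan on day 43 is exactly 6.0 elapsed weeks and meets the SD minimum only with the +1 rule.

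Calling any documented progression PD, however late, is not recommended. It would also relabel patients first shown to progress at C6 or C10 after unusable scans, which is a more debatable convention.

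The cost is one line of text and one programming parameter, with no new data. It is a departure from the generic guideline and must be stated as such. If the primary CSR RAP already sets a suitable limit, a reference to it is enough.
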